Given the significant brain damage and multiple disabling neurological sequelae, in severe TBI patients, combined with the limited efficacy of conventional pharmacological and cognitive rehabilitation interventions, REAC may be a promising therapeutic approach for affected patients. We will conduct a randomized clinical trial to assess REAC's effects in patients with DAI.

GOALS

Primary Endpoint

- To evaluate the qEEG changes in patients with subacute/chronic DAI, following REAC neuromodulation.

Secondary Endpoint

- To evaluate the qEEG changes in adults free of neurological conditions, following REAC neuromodulation.
- To evaluate cognitive and humor changes in adults free of neurological conditions, following REAC neuromodulation.

LITERATURE REVIEW

TBI Classifications

TBI is typically a heterogeneous condition being classified by clinical severity, mechanism of injury and pathophysiology, all of which are relevant to properly determine treatment and prognosis.

From a clinical point of view, TBI is classified as mild, moderate and severe depending on the duration of the loss of consciousness, level of consciousness on the Glasgow Coma scale and the presence or absence of post-traumatic amnesia, as well as its duration. However, knowledge of other information, such as history of exogenous intoxication, use of sedatives and neuromuscular blockers, as well as orotracheal intubation, is essential to avoid misclassification of TBI [41, 42].

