TBI broadly affects the most diverse aspects of memory and presents a striking characteristic: the pattern of memory impairment is much more similar to that found in patients with frontal injury than individuals with amnesia [79]. In 2005, Mathias and Mansfield [80] compared 25 TBI victims with 25 healthy individuals matched for age and sex and found that the patients had worse performance in explicit memory. These same findings have been demonstrated in other studies, indicating memory disorders to be highly prevalent after DAI, affecting up to 40 to 60% of victims of severe TBI. In fact, TBI broadly affects the most diverse aspects of memory and presents a striking characteristic: the pattern of memory impairment is much more similar to that found in patients with frontal injury than individuals with amnesia [79].

Although the pathophysiological mechanism is not well understood, the cognitive changes found in these patients seem to be related to the impairment of circuits involving several neurotransmitters, such as serotonin, glutamate, dopamine, norepinephrine and acetylcholine [81]. In the acute phase of TBI there is a massive production and release of acetylcholine in combination with other neurotransmitters such as glutamate, catecholamines and serotonin, which contributes to the clinical disorders observed at this stage (changes in the level of consciousness, executive dysfunctions and memory impairment) [82, 83]. However, in chronic disorders affecting these cognitive domains, acetylcholine seems to be the most relevant neurotransmitter involved [81, 84]. After experimental studies demonstrated the impairment of cholinergic pathways after TBI in the 1990s, Dewar and Graham and Murdoch *et al.* [85, 86] conducted seminal studies *postmortem* in humans and demonstrated the pathophysiology of cholinergic dysfunctions observed in TBI victims. Despite the relative normalization of most neurotransmitters, cholinergic function remained chronically reduced, which was apparently directly related to the cognitive disorders observed [84-86].

The spontaneous cognitive recovery of DAI victims is well documented in the literature. Despite memory impairment after TBI, many patients have spontaneous recovery of cognitive functions. This is a well-known and reported phenomenon in the medical literature. Zaninotto *et al.*, [87] followed 18 patients with DAI for 12 months after trauma and documented a significant improvement in verbal fluency at the 12th

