Radio Electric Asymmetric Conveyer (REAC) technology is a relatively new approach to neuromodulation, aiming to influence the nervous system through the application of radio electric fields asymmetrically conveyed, using precise administration procedures. These specific treatments have proven useful and effective in numerous mood, behavior and movement control disorders [33-40, 100-134].

MATERIAL AND METHODS

Series

Participants will be prospectively included of both genders, between 18 and 60 years of age. Eligibility criteria is described in Tables 4 and 5.

Table 4 - Inclusion criteria

1.	Clinical-radiological diagnosis of diffuse axonal lesion
2.	Traumatic brain injury suffered for at least one (1) week
3.	Be hospitalized at the neurotraumatology section at the Hospital das Clínicas Complex of the Medical School of the University of São Paulo (HCFMUSP)

Table 5- Exclusion criteria

1.	History of addictive behavior and/or serious psychiatric illnesses
2.	Presence of bone defects in the skullcap
3.	Uncontrolled epilepsy
4.	Carriers of implanted metallic or electronic devices: cardiac pacemaker, stents , epidural or deep brain electrodes, cochlear implants, drug infusion systems or intracranial clips
5.	Next of kin refusal to participate in any of the stages of the study, as well as to be randomly allocated to one of the groups
6.	Next of kin refusal to provide the free and informed consent for participation
7.	Gestation
8.	Severe, uncontrolled systemic disease

	9. Magnetic resonance imaging of the brain with findings not compatible with DAI or demonstrating the presence of expansive intracranial lesion.
--	--

The clinical diagnosis of DAI is defined as a state of coma after TBI, lasting at least 6 hours, after exclusion on imaging of intracranial lesions with mass effect or significant ischemic brain lesions. At hospital admission, all patients underwent head CT as a standardized routine of hospital care for patients with moderate and severe TBI. In addition, all patients underwent magnetic resonance imaging of the brain to identify injuries suggestive of DAI, as well as to rule out other causes of brain injury that could justify the patient's clinical picture.

Recruitment and adherence strategies

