The participants will be recruited when hospitalized at the Neurotraumatology Clinic of the Hospital das Clínicas Complex of the Medical School of the University of São Paulo (HCFMUSP). Overall admission and in-hospital records will be collected of each patient who meet the inclusion criteria. Patients will complete the minimum period of 6 months of TBI of follow-up.

In this study, REAC will be performed a single session of Neuro Postural Optimization (NPO), and 18 Neuro Psycho Physical Optimization – Brain Wave Optimization-G (NPPO-BWO-G) treatment sessions for 4 daily sessions. Each next of kin will receive written instructions with the date and time of the next sessions in order to avoid misunderstandings.

Search locations

The study will be conducted within the HCFMUSP, in São Paulo - SP, which has 2400 beds distributed among its 8 specialized institutes and 2 auxiliary hospitals (www.hc.fm.usp.br). The research locations in the various stages of the study are described in Table 6:

Table 6 - Stages of the study and the respective places where they will be carried out

Stage of the study	Location	Purpose
Patient selection	ICU - Neurotraumatology	
Electroencephalogram	ICU - Neurotraumatology	Brain waves mapping
Brain MRI	Central Institute	DAI diagnostic
REAC	ICU - Neurotraumatology	Intervention

DAI: diffuse axonal injury, ICU: intensive care unit, MRI: magnetic resonance imaging,

REAC: radio-electric asymmetric conveyer.

Study design

This is a prospective, randomized, double-blind, placebo-controlled clinical trial. According to the hypotheses of the present study, the sample size calculation was made considering an alpha error of 5% and based on other studies with similar design [135-140]. We estimate that 30 patients should complete the follow-up and be included in the statistical analyses. However, lack of adherence could be a problem. Thus, we estimate losses at 20% and calculated a final sample size of 36 participants. Subjects with no history of chronic neurological disorders will also be included and separated of DAI patients but submitted to the same protocols. After meeting the eligibility criteria, the participants will follow the steps of the study as described in Table 7.

Table 7 - The study steps

Patient selection	Medical record, radiology, participation consent
Step 1 (pre-intervention)	qEEG, TCD and brain4care up to 3 days before the start of REAC sessions
Step 2 (intervention)	NPO (single session)

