The Kolmogorov-Smirnov test will be used to verify the parametric nature of the quantitative values observed in the battery of neuropsychological tests. The repeated measures related to the items neuropsychological assessment and cortical excitability will be compared through ANOVA-type analyses (*analysis of variance*) of two factors for repeated measures and the interaction test between the groups considered to test the null hypothesis[141, 142].

To compare the delta (Δ) values between the intervention groups, the Mann-Whitney test will be used. The comparison of the frequency of adverse effects according to the intervention groups will be performed using Pearson's chi-square. The Wilcoxon Rank-Sum test will be performed in the intra-group comparison regarding pre-intervention (E1) and post-early intervention (E2) performance in the neuropsychological assessment.

Statistically significant findings are those with a p-value or probability of type I error lower than 5%. The control of blinding will be done with the analysis of agreement with Cohen's kappa. The sample size is based on the TMT part B scores obtained after the intervention (E2). The analyses were performed using *Microsoft Excel* 2010 and *IBM SPSS (Statistical Package for Social Sciences)* v.21.0.

Funding

The present study will receive no funding. Device/software manufacturers will support the project providing their methods to be used in the study.

Chronogram

June 2024- Protocol submission.

Recruitment: One year.

Data analysis: Three months.

Publishing results: Manuscript submission to publication one month later.

References

1. Ghajar J. (2000) Traumatic brain injury. Lancet 356:923-929. [https://doi.org/10.1016/S0140-6736\(00\)02689-1](https://doi.org/10.1016/S0140-6736(00)02689-1)
2. Cole TB. (2004) Global road safety crisis remedy sought: 1.2 million killed, 50 million injured annually. JAMA 291:2531-2532. <https://doi.org/10.1001/jama.291.21.2531>

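### The primary objective names subacute/chronic DAI but entry is limited to inpatients from one week after injury, and the only between-group test of change uses neither baseline qEEG nor time since injury

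*Protocol*

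**What the plan says.** - **Objective (GOALS, Primary Endpoint).** "To evaluate the qEEG changes in patients with subacute/chronic DAI, following REAC neuromodulation". The protocol puts no time limits on either phase.
- **Eligibility (Tables 4 and 5).** A patient must have had "Traumatic brain injury suffered for at least one (1) week" and must "Be hospitalized at the neurotraumatology section at the Hospital das Clínicas Complex". Neither table sets an upper limit on time since injury.
- **Setting (Table 6).** Patient selection, EEG and REAC are all located at "ICU - Neurotraumatology". The Abstract instead places the sessions after ICU discharge. These two statements need reconciling.
- **Timing of the endpoint (Table 7).** qEEG is recorded within 3 days before the first session and within 3 days after the last. The 3- and 6-month visits list mRankin, GOSE and DASS 21, but no qEEG.
- **Randomisation.** Allocation is 1:1 in blocks of four, with no stratification factor named.
- **Statistical analysis.** "To compare the delta (Δ) values between the intervention groups, the Mann-Whitney test will be used". The sentence names no outcome and no covariate. A two-factor repeated-measures ANOVA is also planned, but it is tied to the neuropsychological and cortical-excitability measures and again names no covariate.
- **Background (Cognitive changes due to TBI and treatment).** "The spontaneous cognitive recovery of DAI victims is well documented in the literature".

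**The concern.** There are two linked issues.

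First, the objective and the entry rules describe different populations. Recruitment takes place during the hospital stay, and Table 6 puts selection in the ICU. A patient living at home with long-standing DAI cannot be enrolled. A result worded as the objective is worded would extend to chronic DAI with few or no such patients behind it. The later visits do not repair this, because no qEEG is taken at them.

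Second, the entry rule leaves the recovery phase open from one week upward, and the analysis does nothing with it. The protocol itself treats phase as relevant. It describes secondary injury evolving over hours to weeks, reports altered inhibition in the subacute phase, and lists the phases of TBI among the open questions for neuromodulation. If untreated qEEG change depends on how recent the injury is, that variation enters the error term of a trial with about 15 patients per arm. A chance difference between arms in time since injury would then go uncorrected. Baseline qEEG enters the planned test only through subtraction.

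**Working it through.** **Population, passages side by side.** The objective covers subacute and chronic DAI. Table 4 requires current hospitalisation and at least one week since injury. Table 6 puts selection in the ICU. A chronic outpatient fails Table 4. A long-stay or readmitted inpatient does not. The chronic part of the objective is therefore undefined and probably thin, but not formally excluded.

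**The plan's own figure.** 30 evaluable × 1.20 = 36, which matches the stated final sample size. No effect size, SD or power is given, so the 30 itself cannot be re-derived. At 1:1 it means 15 per arm.

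**What 15 per arm can detect.** Two-sided 5% (sidedness assumed), 80% power, normal approximation: (1.960 + 0.842) × √(2/15) = 2.802 × 0.365 = 1.02 SD of the change score.

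**Value of adjusting for time since injury.** Let R² be the share of the variance of qEEG change that time since injury explains. This is an assumption, as the protocol gives no figure. Estimating one covariate with N = 30 inflates the variance of the arm contrast by 1 + 1/(30 − 4) = 27/26 = 1.038. The equivalent sample is 30/(1 − R²) ÷ 1.038:

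| Assumed R² | 30/(1 − R²) | After covariate cost |
|---|---|---|
| 0 | 30.0 | 28.9 |
| 0.10 | 33.3 | 32.1 |
| 0.20 | 37.5 | 36.1 |
| 0.30 | 42.9 | 41.3 |

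With two covariates (baseline and time) the cost factor is 1 + 2/(30 − 5) = 1.08. If neither explained any of the change, the loss would be to 30/1.08 = 27.8 patients. Any precision from baseline qEEG comes on top of the table and is not counted there.

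**Comparison with the planned test.** The calculation above compares linear models, so a simulation set Mann-Whitney against ANCOVA directly. It used 6,000 runs per cell, 15 per arm, normal data and one covariate whose correlation with change is ρ. The values ρ = 0.3 and 0.5 correspond to R² = 0.09 and 0.25.

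| | ρ = 0.3 | ρ = 0.5 |
|---|---|---|
| Power at 1.02 SD, Mann-Whitney | 74% | 72% |
| Power at 1.02 SD, ANCOVA | 80% | 86% |
| Overall type I error, Mann-Whitney | 4.6% | 4.9% |

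**Chance imbalance.** Without stratification, the arm difference in mean time since injury has SD √(2/15) = 0.365 covariate SDs. The probability that it exceeds 0.5 in either direction is about 17%. An imbalance of 0.5 shifts the unadjusted contrast by 0.5ρ, which is 0.15 or 0.25 outcome SD for ρ = 0.3 or 0.5. Given an imbalance above 0.5, the simulated Mann-Whitney type I error is about 7% or 12%.

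**Availability.** The date of injury must be known to apply the one-week rule, and baseline qEEG is step 1 of Table 7.

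**The case against.** **Spontaneous recovery and validity.** A reader might infer from the background on recovery that the treatment comparison is biased. The documents do not support that. Randomisation against sham balances spontaneous change on average, and the simulated overall type I error stays near 5%. The higher rates apply only to the roughly one trial in six with a marked imbalance. An unadjusted test in a randomised trial is legitimate. This objection stands in full.

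**Different outcome and time scale.** The recovery cited is cognitive, over 6 to 12 months. The qEEG contrast is short: 18 sessions at four a day need 5 days, plus one for the NPO session if it has its own day, plus up to 3 days at each end, so about 5 to 12 days. Nothing in the protocol shows that qEEG change over that interval depends on days since injury. This also stands. It is why R² is an assumption with a range that starts at zero.

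**The two halves pull against each other.** Inpatient entry narrows the spread of time since injury, so the stronger the population mismatch, the smaller the gain from the covariate. This is fair, and it argues for the lower part of the range.

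**Chronic patients are not barred.** A reader might infer that the chronic part of the objective is impossible to meet. With no definition and no upper limit, a long-stay or readmitted inpatient remains eligible. The supportable statement is that chronic outpatients cannot enter and chronic patients will be few or absent.

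**The Mann-Whitney sentence does not name qEEG.** True, and a separate SAP could specify covariates. But it is the only between-group test of change in the protocol. With two time points, the interaction test in the repeated-measures ANOVA is equivalent to a t-test on change, so applying that to qEEG would leave the same gap.

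**DAI grade.** The protocol's outcome figures by severity (favourable in 78%, 59% and 28%) might suggest adjusting GOSE and mRankin for grade as well. The protocol does not show that a grade is recorded. Its pathological grading and its classification by coma duration also differ, so this is not supported.

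**Conclusion.** The objective and the entry rules do not match. That part needs no assumption: it affects what the trial may conclude, and correcting it costs nothing in patients.

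The analysis part is an efficiency point. For an assumed R² of 0 to 0.30, adjusting for time since injury makes 30 analysed patients worth roughly 29 to 41. It also protects against a chance imbalance that occurs at the 0.5 SD level in about 17% of such trials. These figures rest on the assumed R², on 15 analysed patients per arm and on approximately normal data on the analysis scale. They do not indicate bias or an inflated overall error rate. With a detectable difference of about 1.02 SD, precision is scarce enough to make the change worthwhile.

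**What to change.** 1. **Reconcile objective and eligibility.** Define the intended phase in terms of time since injury and make GOALS, Table 4, Table 6 and the Abstract agree, including the ICU and post-ICU wording. The sponsor sets the window. Alternatively, keep the entry rules and limit the objective and conclusion to hospitalised patients at least one week after TBI.
2. **Name the primary qEEG analysis.** For the power measure designated as primary, fit an ANCOVA of post-treatment log power on arm, baseline log power and log days since injury. Use a rank ANCOVA if the log scale does not behave. This replaces the unadjusted comparison of deltas for the primary outcome.
3. **Record days from injury to randomisation** as a baseline variable and report it by arm.

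The cost is a change of wording, two covariates that the design already makes available, and one or two degrees of freedom. At worst, if neither covariate carries any information, the loss is about two patients' worth of precision (30 to 27.8). No extra enrolment or measurement is needed.

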Step 3 (intervention)	NPPO-GW (18 sessions)
Step 4 (post-intervention)	qEEG up to 3 days after the end of REAC sessions

Follow-up discharge, 3m and 6m mRankin, GOSE, DASS 21

qEEG: quantitative electroencephalogram, TCD: transcranial Doppler, REAC: radio-electric asymmetric conveyer, NPO: neuro-postural optimization, NPPO-GW: gamma-waves neuro psycho physical optimization.

Randomization

A participant will select patients according to DAI criteria and obtain consent for participation with the next of kin for each eligible patient. Following, qEEG examinations will be performed. Up to three days after finishing NPPO-BWO sessions, a second acquisition of qEEG will be performed. All participants will be blinded between active and sham until the study is finished.

Participants will be randomly divided in a 1:1 ratio into two groups:

1. Active
2. *Sham*

The randomization process will be done in blocks interchanged, with the size of each block equal to four. The computerized system available in www.randomization.com will be used. For the persistence of allocation concealment, all evaluations will be performed using a database containing the group with a label "A" and "B". Consequently, all analyses were made without possible presumptions as to the allocation of the group.

Masking of Groups

In order to maintain masking in the study, the REAC device has a very similar shape, size, color, weight and emits very similar sounds. The participants and their families will not know which group the patient has been included up to the conclusion of the study. The entire process of selection, interview, neuropsychological evaluation and intervention with REAC will be similar in the groups, differing only the type of device used. The neuropsychologist responsible for the application of the neuropsychological tests will be unaware of the allocation of the intervention group.

Ethics

The project will be submitted to the Research Ethics Committee of the Hospital das Clínicas da Faculdade de Medicina da Universidade de São Paulo.

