Patients will be submitted qEEG testing before starting the REAC protocols and then after finishing the last session. For data collection, EEG examinations were performed using an international 10-20 electrode placement system. The examination will last 30 minutes, 15 minutes with eyes open and 15 minutes with eyes closed (relaxed wakefulness. The digital 19-channel Nihon Kohden® EEG 1200 version 01.71 (Nihon Kohden, Tokyo, Japan) will be used., The channels follow the 10-20 system: seven located in the frontal lobe (Fz, Fp1, Fp2, F3, F4, F7 and F8), three in the center (Cz, C3 and C4), four in the temporal lobe (T3, T4, T5 and T6), three in the parietal lobe (Pz, P3 and P4) and two in the occipital lobe (O1 and O2). For quantitative analysis, the data were converted using the Neuromap of the Neuroworkbench software, transferred to Matlab vR2002b and treated with the EEGLab v2023.0116 software. After being imported into EEGLAB, the spatial coordinates of each electrode will be inserted according to the 10-20 system. The signals were referenced using the average between the channels. The baseline was automatically removed using a 0.5Hz 117 high-pass filter. Artifacts are automatically rejected and incorrect data periods removed. Finally, the Independent Component Analysis is performed.

Processing

Using EEGLab's Darbeliai tool, the power spectral density of each channel is calculated for four bands: delta (1-4 Hz), theta (4-8 Hz), alpha (8-13 Hz), beta (13-32 Hz), in which the absolute power will be determined. The relative power analysis will be performed using the Fast Fourier Transform FFT.

OUTCOMES

Primary:

Observe if there are significant changes in the electroencephalographic pattern, compared between the groups.

Secondary:

Observe if there are:

Significant clinical improvement determined by the mRankin and GOSE scales between the groups.

Statistical analysis

Categorical variables will be presented in absolute values and relative frequencies, while continuous variables will be described in measures of central tendency and dispersion. All analyses will be performed under the intention to treat.

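### Enrolling 36 with 20% losses is expected to leave 28 to 29 analysable patients, not the 30 the protocol asks for

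*Protocol*

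**What the plan says.** Three figures in the protocol's Study design section bear on this point.

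- The number wanted at the end: "We estimate that 30 patients should complete the follow-up and be included in the statistical analyses".
- The reason for an allowance: "However, lack of adherence could be a problem".
- The allowance and the resulting target: "we estimate losses at 20% and calculated a final sample size of 36 participants".

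No inflation formula is shown, and no other loss rate or enrolment target appears elsewhere in the protocol. The 30 and the 36 concern the DAI patients; the neurologically healthy volunteers are a separate group and do not count towards either number. The Randomization section gives 1:1 allocation in blocks of four. The Statistical analysis section adds: "All analyses will be performed under the intention to treat".

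**The concern.** The 30 is a number after losses, the 36 is a number before losses, and the 20% is meant to link them. On the usual meaning of a loss rate, a share of those enrolled, it does not. A 20% loss from 36 takes the trial below 30. The slip is a familiar one: multiplying the completers by one plus the loss rate, when they should be divided by one minus it.

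What is at stake is modest. The enrolment target is a headline design figure, and anyone who multiplies 36 by 0.80 will see that it does not give 30. If losses run as planned, the trial would report fewer analysable patients than it said it needed, although nothing had gone wrong in its conduct.

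**Working it through.** **Inputs**

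- Completers wanted: n = 30 (Study design).
- Loss rate: d = 0.20 (Study design).
- Enrolment target: N = 36 (Study design).
- Allocation 1:1, block size 4 (Randomization).

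**Reproducing the protocol's figure**

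n × (1 + d) = 30 × 1.20 = 36. This matches exactly.

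**The figure that meets the stated aim**

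n / (1 − d) = 30 / 0.80 = 37.5, rounded up to 38 (19 per arm). Check: 38 × 0.80 = 30.4.

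**What 36 is expected to deliver**

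- Expected completers: 36 × 0.80 = 28.8, or 14.4 per arm, against 15 per arm intended.
- Expected shortfall: 30 − 28.8 = 1.2 patients.
- Largest loss at which 36 still gives 30: 1 − 30/36 = 16.7%.

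**Chance of reaching at least 30 completers**

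Assumption: each patient is lost independently with probability 20%, so the number of completers is binomial (N, 0.80).

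| Enrolled | Expected completers | Chance of 30 or more | Blocks of four |
|---|---|---|---|
| 36 | 28.8 | 40% | 9 |
| 38 | 30.4 | 66% | 9.5 |
| 40 | 32.0 | 84% | 10 |

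**Effect on power, for scale only**

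The protocol states no power, effect size or standard deviation, so these must be assumed. Take a two-arm comparison of means, two-sided alpha of 5% and a normal approximation, where power is about Φ(δ√(m/2) − 1.96), with m patients per arm and standardised effect δ.

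| Assumed δ | m = 15 | m = 14.4 | Difference |
|---|---|---|---|
| 1.0 | 78.2% | 76.5% | 1.7 points |
| 0.8 | 59.1% | 57.4% | 1.7 points |

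**The case against.** The best case for leaving the text alone has four parts.

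*The 20% may be an allowance on the 30.* Six extra patients on a base of 30 is 20%, and on that reading the three numbers agree. But the protocol speaks of losses and blames poor adherence. A loss rate normally refers to those enrolled, and nothing in the text says otherwise. If the other meaning was intended, the sentence needs to say so. The reading shows that the figures can be made to agree; it does not show that the present text is clear.

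*The analysis is by intention to treat, and the second qEEG comes within three days of the last session.* Patients lost later, before the 3- or 6-month visits, would still contribute to the primary comparison. This stands as far as it goes: the shortfall in primary-outcome data may be smaller than 1.2 patients. It does not reconcile the figures, because the Study design section itself ties the 30 to patients who finish follow-up and are analysed.

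*The 30 is itself approximate.* It is presented as an estimate resting on a 5% alpha and on similar studies, and it cannot be reproduced from the protocol. So no precise consequence can be attached to falling about one short. That limits the weight of the point and leaves the arithmetic as it is.

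*A target of 36 fits the blocks.* It makes nine complete blocks, whereas 38 leaves one incomplete. This is fair, and it is a reason to consider keeping 36 or going to 40.

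**Conclusion.** The concern holds: the enrolment target is wrong as written. At a 20% loss among those enrolled, 36 patients are expected to yield 28 to 29 completers, not 30, and 30 would require 38. The conclusion rests only on the protocol's three numbers and on the ordinary meaning of a loss rate. The 40% chance of reaching 30 also assumes independent losses; on that assumption the trial is more likely to miss its stated number than to reach it.

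The size is small: about one completer, two more patients to enrol, and under the assumed effects less than two points of power. No analysis or decision rule changes. It is a cheap correction to a stated design figure and not a threat to the trial.

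**What to change.** Revise the sentence in the Study design section so that the three figures agree. Any of these will do:

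1. Keep 36 and say that 28 to 29 evaluable patients are expected at 20% loss. This costs nothing but a slightly less favourable figure, and it keeps nine whole blocks.
2. Keep 36 and 30 and state the loss rate as 16.7%, if the investigators consider that rate realistic.
3. Keep 30 and 20% and raise the target to 38, or to 40 so that the last block of four is filled. This costs two or four more patients.

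The first is enough to make the protocol consistent.

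### Fixed, disclosed blocks of four let anyone who sees earlier A/B labels in order deduce, on average, one third of the next labels; varying the block size would largely remove that

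*Protocol*

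**What the plan says.** All statements are in the protocol.

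- **Randomization:** "Participants will be randomly divided in a 1:1 ratio into two groups", active and sham. On the method: "The randomization process will be done in blocks interchanged, with the size of each block equal to four". A public website generates the list. No other block size and no strata are mentioned.
- **Randomization, on concealment:** the one measure offered is that "all evaluations will be performed using a database containing the group with a label" of A or B. The same section has one study role selecting patients and obtaining consent from the next of kin, and keeps active/sham status masked until the study ends.
- **Masking of Groups:** the procedures are alike in both arms, "differing only the type of device used". The devices are described as very similar in appearance and sound.
- **Search locations:** "The study will be conducted within the HCFMUSP, in São Paulo - SP". Table 6 places patient selection, EEG and the REAC sessions in the same neurotraumatology ICU.
- **Study design:** "Thus, we estimate losses at 20% and calculated a final sample size of 36 participants".

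**The concern.** Allocation concealment means that whoever enrols the next patient cannot know what that patient will receive. Masking means that people do not know which arm a treated patient is in. The A/B label serves masking. It does not serve concealment, because it shows which earlier patients share a group. With a known block length of four and a single list, that is the information needed to work out how a block must end.

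Foreknowledge matters when it can be acted on. Table 4 requires at least one week since injury and sets no upper limit, so an enrolment could be brought forward or held back while the patient is on the unit without breaching eligibility. The Clinical Aspects section reports favourable evolution in 78% of mild and 28% of severe DAI, and no stratification by severity is described. With about 18 patients per arm, moving a few patients could unbalance the groups on prognosis.

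**Working it through.** The protocol gives no predictability figure, so there is none to reproduce.

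**Inputs:** block size 4, fixed (Randomization); ratio 1:1 (Randomization); one centre (Search locations); 36 patients (Study design), taken as given. Number of blocks: 36/4 = 9. This assumes that the volunteers without neurological disease, whom Study design separates from the DAI patients, are not on the same list. The protocol does not settle that.

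**Condition:** the observer sees all earlier labels in enrolment order and knows where blocks begin.

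**Labels that are certain in advance.** There are C(4,2) = 6 equally likely blocks. A label is certain once the other letter has been used twice in the block.

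| Blocks | Certain labels in each |
|---|---|
| AABB, BBAA | 2 (third and fourth) |
| ABAB, ABBA, BAAB, BABA | 1 (fourth) |

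- Total: 2 × 2 + 4 × 1 = 8 of 24 positions = 1/3, or 4/3 per block.
- For 9 blocks: 9 × 4/3 = 12 expected.
- Each block contributes 2 with probability 1/3 and 1 otherwise, so SD = √(9 × 1/3 × 2/3) = √2 ≈ 1.4.
- Possible range: 9 × 1 = 9 to 9 × 2 = 18, that is 25% to 50% of the 36.

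**Best guess (always name the letter used less so far in the block).** Probability of being right, by position:

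- first: 1/2
- second: 2/3
- third: 1/3 × 1 + 2/3 × 1/2 = 2/3
- fourth: 1

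Mean = (1/2 + 2/3 + 2/3 + 1)/4 = (17/6)/4 = 17/24 = 70.8%, against 50% by chance.

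**Comparison with varying sizes.** This was simulated for 36 patients with sizes 4 and 6 chosen with equal probability. The observer sees all earlier labels and knows that the sizes are 4 or 6, but not which applies to a given block.

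| Scheme | Certain | Best guess right |
|---|---|---|
| Fixed 4 | 33.3% (12 of 36) | 70.8% |
| Random 4 and 6 | about 5.6% (about 2 of 36) | about 68.9% |

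Varying the size therefore removes most of the certainty but little of the guessing advantage of someone who sees every earlier label. Withholding the labels from the enrolling person removes both: without sight of earlier labels, no assignment is certain to that person.

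**The case against.** **A reader might infer that one third of assignments are known in advance to the person recruiting.** The protocol does not support that. It gives the A/B database to evaluators and analysts. It does not say that the person who selects and consents patients sees it, sees it during recruitment, or sees labels in enrolment order. It is also silent on whether that person is kept from the labels. Access is plausible at a single unit but not established.

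**A reader might infer that the next arm is known.** Only the letter can be deduced. While the masking holds, knowing that the next label is A says nothing about active or sham, so steering better-prognosis patients towards active treatment needs the code to be broken as well. One unmasked patient or one recognised device would break it for the whole list. That is a further condition, not a stated fact.

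**A reader might infer that the devices give the allocation away.** The text says that the devices differ between arms and are very similar. It does not say that staff can tell them apart or that recruiters attend sessions.

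**A reader might infer that no safeguard exists.** The protocol describes no other mechanism, which is different. Who holds the list and how assignments are released may be set out in operational documents, and their absence here is not the point.

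Fixed blocks of four are also a legitimate choice and give exactly 18 per arm at 36. All of this limits the claim. What stands is that the protocol fixes and discloses a single block size, and that the measure it offers as concealment does not hide the next assignment.

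**Conclusion.** The point holds as a minor weakness of design, not as evidence that allocation is or will be subverted. If earlier labels are seen in order, an expected 1/3 of labels (12 of 36, range 9 to 18) can be deduced and 70.8% can be guessed. The figure of 12 assumes nine complete blocks used by the DAI patients only; the 1/3 and 70.8% hold for any number of complete blocks of four. If the enrolling person does not see the labels, none is certain to that person. Bias towards one arm would additionally require that the A/B code be broken. Because the protocol itself fixes the block size, this is not a detail left to another document.

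**What to change.** In the Randomization section, replace the fixed block of four with randomly varying block sizes, for example 4 and 6, and leave the sizes out of documents available to recruiting staff. State that earlier A/B labels are kept from whoever selects and consents patients, and describe the A/B label as a masking measure rather than as concealment. If enrolment has begun, apply the change to the blocks still to be issued and record who could see the labels until then.

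No extra patients or procedures are needed. The cost is that recruitment may end inside a block: with a largest block of six, the arms can differ by up to three patients, whereas nine complete blocks of four give 18 and 18.
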